## **7.2. Participant Withdrawal From the Study**

A participant may withdraw from the study at any time at their own request or may be withdrawn at any time at the discretion of the investigator for safety, behavioral, compliance, or administrative reasons.

If a participant withdraws from the study, they may request destruction of any samples taken and not tested, and the investigator must document this in the site study records. If the participant withdraws consent for disclosure of future information, the sponsor may retain and continue to use any data collected before such a withdrawal of consent.

See [Table 3](#) for data to be collected at the time of study withdrawal and follow-up and for any further evaluations that need to be completed.

### **7.3. Lost to Follow-Up**

A participant will be considered lost to follow-up if they repeatedly fail to return for scheduled visits and are unable to be contacted by the study site.

The following actions must be taken if a participant fails to return to the clinic for a required study visit:

- The site must attempt to contact the participant and reschedule the missed visit as soon as possible and counsel the participant on the importance of maintaining the assigned visit schedule and ascertain whether or not the participant wishes to and/or should continue in the study.
- Before a participant is deemed lost to follow-up, the investigator or designee must make every effort to regain contact with the participant (where possible, 3 telephone calls and, if necessary, a certified letter to the participant's last known mailing address or local equivalent methods). These contact attempts should be documented in the participant's medical record.
- Should the participant continue to be unreachable, they will be considered to have withdrawn from the study.

## 8. STUDY ASSESSMENTS AND PROCEDURES

### 8.1. Administrative and General Procedures

#### 8.1.1. Informed Consent Process

- The investigator or their representative will explain the nature of the study to the participant or their legally authorized representative and answer all questions regarding the study.
  - Informed consent must be obtained before any study-related procedures are conducted, unless otherwise specified by the Protocol.
  - Informed consent must be obtained using the IRB/IEC-approved version in a language that is native and understandable to the participant. An ICF template will be provided by the sponsor or its designee. The sponsor or its designee must review and acknowledge the site-specific changes to the ICF template. The ICF must include a statement that the sponsor or its designee and regulatory authorities have direct access to participant records.
  - The ICF must contain all required elements including optional samples/procedures (eg, optional biopsy) and describe the nature, scope, and possible consequences of the study in a form understandable to the study participant.
- Participants must be informed that their participation is voluntary. Participants or their legally authorized representative will be required to sign a statement of informed consent that meets the applicable requirements and regulations for the country(ies) in which the study is being conducted as well as the IRB/IEC or study center.
- The participant must be informed that their personal data collected for the study will be used by the sponsor and/or their designee(s) in accordance with local data protection laws. The level of disclosure must also be explained to the participant.
- The participant must be informed that their medical records may be examined by Clinical Quality Assurance auditors or other authorized personnel appointed by the sponsor, by appropriate IRB/IEC members, and by inspectors from regulatory authorities.
- The medical record must include a statement that written informed consent was obtained before the participant was enrolled in the study and the date the written consent was obtained. The authorized person obtaining the informed consent must also sign the ICF.
- Participants must provide consent to the most current version of the ICF during their participation in the study.
- A copy of the ICF(s) must be provided to the participant or the participant's legally authorized representative.
- Participants who are rescreened are required to sign a new ICF and must be assigned a new participant ID number.

### **8.1.2. Screening Procedures**

Screening is the interval between signing the ICF and the day the participant is enrolled in the study (Day 1). Screening may not exceed 28 days. Assessments that are required to demonstrate eligibility may be performed over the course of 1 or more days during the screening process.

Procedures conducted as part of the participant's routine clinical management (eg, blood counts or physical examinations) and obtained before signing of the ICF may be used for screening or baseline purposes provided that the procedure meets the Protocol-defined criteria and has been performed in the timeframe of the study (ie, within 28 days or less prior to Day 1). For participants who are enrolled in the study, information associated with eligibility requirements must be entered into the appropriate eCRF pages.

Results from the screening visit evaluations will be reviewed to confirm eligibility before randomization and the administration of study drug. Tests with results that fail eligibility requirements may be repeated once during screening if the investigator believes the results to be in error. For screening assessments that are repeated, the most recent available result before randomization will be used to determine eligibility.

See Sections [5.4](#) and [5.5](#) for information regarding screen failures and replacement of participants, respectively.

### **8.1.3. Interactive Response Technology Procedure**

Each participant will be identified in the study by a participant ID number, which is a combination of a country's abbreviation, the site ID, and the participant ID number. Site staff should contact the IRT to obtain the participant ID number during screening.

Upon determining that the participant is eligible for study entry, the IRT will be contacted to obtain the treatment assignment. Additionally, the IRT will be contacted at each regular study visit during both the DBVC period and the OLE period to update the study drug supply. Additional details are provided in the IRT Manual.

### **8.1.4. Distribution of Reminder Cards and/or Diaries**

Participants will be provided with a reminder card starting on Day 1 and at all DBVC and all OLE visits through Week 32. The reminder card will indicate the date and time of the next visit.

Participants will be instructed on the use of the eDiary at the screening visit. The participant will start using the eDiary for completion of the Skin Pain NRS and Itch NRS at screening and for recording study drug applications on Day 1. [REDACTED]

[REDACTED]. Daily study drug administration will be recorded in the eDiary and verified by the study investigator/designee at study visits as shown in [Table 3](#).

### **8.1.5. Demography and Medical History**

#### **8.1.5.1. Demographics and General Medical History**

Demographic data and general medical history will be collected at screening by the investigator or qualified designee and will include year of birth/age, race, ethnicity, medical and surgical

history, and current illnesses. Medical history will include relevant medical and surgical treatments considered to be clinically significant by the investigator.

As race and/or ethnicity data are not to be analyzed from a scientific or medical perspective, but rather are to be reported in a descriptive format only in the CSR, data on race and/or ethnicity from France must not be collected as per GDPR and local data protection law and requirements.

#### **8.1.5.2. Disease Characteristics and Treatment History**

A disease-targeted medical and treatment history will be collected at screening. Details regarding the participant's HS, including date of diagnosis, relevant disease characteristics, and prior treatments, and the reason for stopping treatments, including systemic treatments, and surgical procedures, will be recorded.

### **8.2. Efficacy Assessments**

#### **8.2.1. Lesion Counts**

The HS lesion counts will be assessed at each study visit ([Table 3](#)) by the investigator and used for calculation of efficacy parameters as follows: AN counts (Section [8.2.1.1](#)), HiSCR (Section [8.2.1.2](#)), IHS4 (Section [8.2.1.3](#)), [REDACTED].

[REDACTED]  
[REDACTED]  
[REDACTED]

Definitions and schematics of various HS lesions ([Frew et al 2021](#)) are provided in [Table 7](#) to aid in the identification of the different morphologies.

**Table 7: Definition of Hidradenitis Suppurativa Lesions**

HS Lesion	Definition	Schematic
Abscess	A tender, fluctuant (compressible), palpable lesion, with erythema.	
Inflammatory nodule	A solid, spherical, palpable lesion >1 cm; tender and/or erythematous. Note: a noninflammatory nodule is defined as nontender, nonerythematous nodule.	
Tunnel (nondraining)	Compression of surrounding structures does not elicit drainage of contents.	
Tunnel (draining) a	A linear tract that may open onto the skin surface; drainage expressed at rest or with compression of surrounding structures.	

Note: Definitions and lesion schematics obtained from [Frew et al 2021](#) ("tunnels may include connection to a hollow organ (eg, bladder, intestine) (A), blind ending (B), 2 skin-to-skin openings (C), and no opening to the surface (D). The original artwork was created by Bradley Winters, Penn State University").

a Excluded from this study.

### 8.2.1.1. Abscess and Inflammatory Nodule Counts

The AN counts will be recorded at all visits. The AN results will be used to calculate change in AN count relative to baseline, as well as AN50, AN75, AN90, and AN100, defined respectively as at least a 50%, 75%, 90%, and 100% decrease in AN count relative to baseline.

### 8.2.1.2. Hidradenitis Suppurativa Clinical Response

The HiSCR was originally developed based on the underlying Phase 2 trial of adalimumab and validated against meaningful changes in pain score and DLQI ([Kimball et al 2016](#), [Sabat et al 2020](#)). The achievement of HiSCR is defined as at least 50% reduction in AN count with no increase in either abscess or draining fistula counts, relative to baseline. In this study, participants with draining fistulas (tunnels) will be excluded from the study. Should a randomized participant develop a draining tunnel during the study, the participant will be discontinued from the study.

### 8.2.1.3. International Hidradenitis Suppurativa Severity Score System

The IHS4 ([Zouboulis et al 2017](#)) is a composite, dynamic score, and validated tool used to determine HS severity. It employs a weighted scale using the number of inflammatory nodules, the number of abscesses, and the number of draining tunnels (fistulas or sinuses), with respective weight factors of 1, 2, and 4 (Example: IHS4 score equals the number of inflammatory nodules

[multiplied by 1] plus the number of abscesses [multiplied by 2] plus the number of draining tunnels [multiplied by 4]).

[REDACTED]

[REDACTED]

[REDACTED]

[REDACTED]

### **8.2.2. Hurley Stages of Hidradenitis Suppurativa**

The Hurley classification is a static score and was originally designed for selection of the appropriate treatment modality in a certain body location (Zouboulis et al 2017): medical therapy for Stage I, local surgery for Stage II, and wide surgical excision for Stage III (see [Table 8](#)). Participants who have been diagnosed with HS, Hurley Stage I or II as per inclusion criterion, will be enrolled into the study. The investigator (or designee) will determine the Global Hurley Stage in each affected anatomical region at the designated study visits listed in [Table 3](#).

**Table 8: Hurley Stages of Hidradenitis Suppurativa**

Hurley Stage	Description
I	Abscess formation, single or multiple, without sinus tracts and cicatrization/scarring.
II	One or more widely separated recurrent abscesses with tract formation and cicatrization/scarring.
III	Multiple interconnected tracts and abscesses across the entire area, with diffuse or near diffuse involvement.

### **8.2.3. Body Surface Area**

Total %BSA affected by HS will be used to determine the number of tubes of study drug dispensed at each visit. Total %BSA affected will be estimated at each visit as outlined in the SoA (see [Table 3](#)). Body surface area assessment will be approximated to the nearest 0.1% using the Palmar Method as a guide, with the palm plus 5 digits, with fingers tucked together and thumb tucked to the side (handprint), considered as 1% BSA and the thumb as 0.1% BSA.

### **8.2.4. Patient-Reported Outcomes**

Patient-reported outcomes will be assessed as outlined in the SoA (see [Table 3](#)).

All PROs will be collected via electronic eCOA solution. Sites will be provided with training materials and instructions on the use of eCOA solution and will be responsible to train participants on eDiary use and eCOA completion. Further details on use of the eCOA devices will be provided in respective study documentation.

For PROs scheduled to be completed at study visits: At Day 1, participants will complete PROs after eligibility is met. For subsequent visits after randomization, questionnaires will be completed by the participant before site personnel perform any clinic assessments to avoid biasing the participant's response

For more information, contact the Office of the Vice President for Research and Economic Development at [contact] or [[contact]](mailto:[contact]).

11. *What is the primary purpose of the following statement?*

For more information, contact the Office of the Vice President for Research and Economic Development at [contact] or [[contact]](mailto:[contact]).

Digitized by [contact]

© 2019 Pearson Education, Inc.

11. **What is the primary purpose of the *Journal of Clinical Endocrinology and Metabolism*?**

## 8.3. Safety Assessments

Planned timepoints for all safety assessments are provided in the SoA in [Table 3](#).

See Section [6.5](#) for guidelines regarding the management of relevant laboratory or other safety assessment abnormalities.

### 8.3.1. Adverse Events

Adverse events will be monitored from the time the participant signs the ICF until at least 30 days after the last application of study drug. Adverse events for enrolled participants that begin or worsen after informed consent should be recorded on the Adverse Events Form in the eCRF regardless of the assumption of a causal relationship with the study drug. Conditions that were already present at the time of informed consent should be recorded on the Medical History Form in the eCRF. Adverse events (including laboratory abnormalities that constitute AEs) should be described using a diagnosis whenever possible rather than by individual underlying signs and symptoms.

Adverse events will be reported by the participant (or, when appropriate, by a caregiver, surrogate, or the participant's legally authorized representative). The investigator and any qualified designees are responsible for detecting, documenting, and recording events that meet the definition of an AE or SAE and remain responsible for following up on AEs that are serious, that are considered related to the study drug/procedures, or that caused the participant to discontinue the study drug. Care will be taken not to introduce bias when detecting AEs and/or SAEs. Open-ended and nonleading verbal questioning of the participant, such as "How are you feeling?", is the preferred method to inquire about AE occurrences. Adverse events may also be detected when they are volunteered by the participant during the screening process or between visits or through physical examinations, laboratory tests, or other assessments. The definition, reporting, and recording requirements for AEs are described in Section [9](#).

All SAEs will be reported to the sponsor or designee within 24 hours. The investigator will submit any updated SAE data to the sponsor within 24 hours of it being available.

After the initial AE/SAE report, the investigator is required to proactively follow each participant at subsequent visits/contacts. All SAEs will be followed until resolution, stabilization, the event is otherwise explained, or the participant is lost to follow-up (as defined in Section [7.3](#)).

### 8.3.2. Physical Examinations

At the screening visit and the Week 32/ET2 visit, a comprehensive physical examination should be conducted. The comprehensive physical examination will include assessment(s) of the following organ or body systems: skin; head, eyes, ears, nose, and throat; thyroid; lungs; cardiovascular system; abdomen (liver, spleen); extremities; and lymph nodes; as well as a brief neurological examination. In addition, a participant's height and weight will be obtained during the screening visit.

During the study, a targeted physical examination may be conducted by the investigator or medically qualified designee (per institutional policies and local standard of care) to assess AEs, symptoms/signs, laboratory abnormalities, or other findings. Findings from the targeted physical examination should be reported on the AE eCRF.

### **8.3.3. Vital Signs**

Vital sign measurements (to be taken at each study visit and before blood collection for laboratory tests) include blood pressure, pulse, respiratory rate, and body temperature. Blood pressure and pulse will be taken with the participant in the sitting position after 5 minutes of rest. Abnormal vital signs can be repeated after a rest period at the discretion of the investigator. Abnormal vital sign results identified after the first dose of study treatment, including those that worsen from baseline, considered clinically significant in the medical and scientific judgment of the investigator (ie, not related to progression of underlying disease) are to be reported as an AE.

### **8.3.4. Laboratory Assessments**

See [Table 9](#) for the list of clinical laboratory tests to be performed and [Table 3](#) for the timing and frequency. A central laboratory will perform all clinical laboratory assessments for safety (eg, blood chemistries or hematology assessments) [REDACTED]

[REDACTED] Additional testing may be required by the sponsor based on emerging safety data. All Protocol-required laboratory assessments must be conducted in accordance with the Laboratory Manual. Information regarding collection, processing, and shipping of samples for laboratory assessment is provided in the Laboratory Manual.

Clinically significant abnormal laboratory findings are those that are not associated with the underlying disease, unless judged by the investigator to be more severe than expected for the participant's condition. All laboratory tests with values considered clinically significantly abnormal during participation in the study or within 30 days after the last application of the study drug should be repeated until the values return to normal or baseline or are no longer considered clinically significantly abnormal by the investigator or medical monitor.

See Section [9.1](#) for information regarding laboratory abnormalities that should be recorded as an AE in the eCRF.

**Table 9: Required Laboratory Analytes**

Chemistry	Hematology	Serology	Pregnancy Testing
ALT	Complete blood count, including:	Hepatitis B surface antigen	Human chorionic gonadotropin (WOCBP only)
AST		HCV antibody	
Glucose		HIV antibody	
Creatine kinase			
Creatinine			
Total bilirubin			
Direct bilirubin (if total bilirubin is elevated above ULN)	• Hemoglobin • Hematocrit • Platelet count • Red blood cell count • White blood cell count	HBV-DNA a HCV-RNA b	FSH (women of nonchildbearing potential only)
	Differential count, including: • Basophils • Eosinophils • Lymphocytes • Monocytes • Neutrophils	Other hsCRP	Female participants of childbearing potential only require a serum test at screening and a urine pregnancy test at all other visits. A positive urine test will be confirmed by a serum test.

Note: Additional tests may be required, as agreed by investigator and sponsor, based on emerging safety data or to rule out a diagnosis.

a Reflex testing if Hepatitis B surface antigen is positive.

b Reflex testing if HCV antibody is positive.

#### 8.3.4.1. Pregnancy Testing

A serum pregnancy test will be required for all WOCBP during screening. Urine pregnancy tests will be performed locally, as outlined in the SoA (see [Table 3](#)), and as medically indicated (eg, in case of loss of menstrual cycle or when pregnancy is suspected).

If a urine pregnancy test is positive, the results must be confirmed with a serum pregnancy test. If the serum pregnancy test is negative after a urine test was positive, the investigator will assess the potential benefit/risk to the participant and determine whether it is in the participant's best interest to resume study drug and continue participation in the study.

If a pregnancy is confirmed by a serum pregnancy test, see [Section 9.8](#) for reporting requirements.

#### 8.3.4.2. Serology

HIV and hepatitis screening assessment will be performed at the screening visit (see [Table 3](#)). Generally, virology and serology tests should be performed early in the screening process due to the length of time needed to obtain the results. Additional tests may be performed if clinically indicated.

[REDACTED]

[REDACTED]  
[REDACTED]  
[REDACTED]  
[REDACTED],  
[REDACTED]  
[REDACTED].  
[REDACTED]

## **8.5. [REDACTED] Translational Assessments**

[REDACTED]  
[REDACTED]  
[REDACTED]  
[REDACTED]  
[REDACTED]

### **8.5.2. Photography**

At select sites, photographs of the HS lesion (identified as target lesion), will be taken at visits indicated in [Table 3](#). Detailed methods for capturing photographs will be provided in the Study Manual.

## **8.6. Unscheduled Visits**

Unscheduled visits may occur at any time medically warranted, including when participants develop new lesions of HS. Any assessments performed at those visits should be recorded in the eCRF.

## **8.7. End of Treatment and Early Termination**

The EOT coincides with the Week 32 visit. A participant that completes the Week 32 visit will have reached the EOT with study drug.

If a decision is made that the participant will permanently discontinue study drug prior to the Week 32 visit, then the ET visit should be conducted. If the ET visit coincides with a regular study visit, then the ET evaluations will supersede those of that scheduled visit, and the data should be entered in the ET page in the eCRF. If this decision does not coincide with a regular visit, reasonable efforts should be made to have the participant return to the site to complete the ET procedures.

## **8.8. Follow-Up**

### **8.8.1. Safety Follow-Up**

The safety follow-up period is the interval between the Week 32/ET visit and the scheduled follow-up visit, which should occur 30 days (+ 7 days' visit window) after the Week 32/ET visit (or 30 days after the last application of study drug if the Week 32/ET visit was not performed). Participants who have been in an observation/no treatment cycle from Week 28 or earlier until Week 32 do not need to complete the safety follow-up visit.

Adverse events and SAEs must be reported up until 1) at least 30 days after the last application of study drug or 2) until toxicities resolve, return to baseline, or are deemed irreversible, whichever is longer. Reasonable efforts should be made to have the participant return for the follow-up visit and report any AEs that may occur during this period.

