**Table 3: Schedule of Activities (Continued)**

Visit Day (Range)	Screening	Baseline (Day 1)	Treatment (vehicle-controlled period)					Treatment (open-label extension) a				Follow-up 30 days (+ 7) days after last application		
	Days -28 to -1		Wk 2 (± 3 d)	Wk 4 (± 3 d)	Wk 8 (± 3 d)	Wk 12 (± 3 d)	Wk 16 a ± 3 d/ ET1	Wk 20 (± 3 d)	Wk 24 (± 3 d)	Wk 28 (± 3 d)	Wk 32 (± 3 d/ ET2)			
Patient-reported outcome (continued)														
Laboratory assessments														
Chemistry assessments	X	X e					X				X	X f		
Hematology assessments	X	X e					X				X	X f		
hsCRP		X			X		X				X			
FSH g	X													
Serum Pregnancy test h	X											X		
Urine Pregnancy test h		X		X	X	X	X	X	X	X				
HIV/Hepatitis Serology	X													
Translational assessments														
Photography (at selected sites)		X			X		X				X			

a All Week 16 assessments must be completed before the participant can continue in the OLE.

b Comprehensive physical examination at screening and Week 32/ET2 visit. The comprehensive physical examination will include assessment(s) of the following organ or body systems: skin; head, eyes, ears, nose, and throat; thyroid; lungs; cardiovascular system; abdomen (liver, spleen); extremities; and lymph nodes; as well as a brief neurological examination.

c A targeted physical examination may be conducted at Week 16. Targeted physical examination can be done for assessment of AE and during other visits including unscheduled visit as per discretion of the investigator. A targeted physical examination should only be conducted as indicated by symptoms reported by the participant, AEs, or other findings.

d Total HS BSA (excluding the scalp) should be ≤ 20% to be eligible for study entry and continued participation.

e Not necessary if screening assessment performed within 14 days of Day 1.

f Laboratory assessment is optional during unscheduled visits based on investigator's discretion and clinical judgement.

g Women of nonchildbearing potential only. Follicle-stimulating hormone is not needed in women with a documented hysterectomy, documented bilateral salpingectomy, or documented bilateral oophorectomy.

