h Female participants of childbearing potential will have a serum test at screening and follow-up and a urine test at other visits noted. A positive urine test must be confirmed by a serum test.

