Between OLE study visits, participants will treat all areas identified with HS lesions (total affected area not to exceed 20% BSA). If all signs and symptoms of HS resolve between study visits, the participant will contact the investigator to confirm that study drug applications should be stopped 3 days after the HS lesion (AN count = 0) have disappeared. If this 3-day window is during a study visit and the AN count = 0, Skin Pain NRS = 0, as assessed by the investigator, treatment is to be stopped at the study visit.

Multiple cycles of treatment/no treatment may be utilized as needed and treatment start/stop dates should be recorded in the eDiary. If a participant has stopped treatment during the OLE period, treatment may be restarted after consultation with the investigator if the participant has an AN count  $\geq 1$  and/or pain (Skin Pain NRS score  $\geq 1$ ). Approval to treat additional areas may occur via telephone during the OLE period, although the investigator, at their discretion, may ask the participant to return for an unscheduled visit.

At any time during the OLE period, if a participant's new areas to be treated in addition to the areas already identified at the previous visit exceed 20% BSA, then the participant should be discontinued from study treatment and the ET assessment should be completed. The amount of

study drug used per application will be determined by weighing a tube before and after the participant applies study drug to the affected areas. All tubes (including caps) of study cream will be weighed before being dispensed. All returned tubes (including caps) of study cream will also be weighed.

**Table 5** presents the study treatment information.

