9.2. Adverse Events

9.2.1. Adverse Event Definitions

A TEAE is any AE either reported for the first time or worsening of a pre-existing event after first application of study drug and within 30 days of the last application of study drug. For participants who cross over treatments, the first application date is period-specific; the end date is 30 days after the last application date in this period, or the first application date in the next period, whichever comes first. Analysis of AEs (as discussed below) will be limited to TEAEs, but data listings will include all AEs regardless of their timing in relation to study drug application.

Adverse events will be tabulated by MedDRA PT and SOC. Severity of AEs will be graded using the National Cancer Institute CTCAE v5.0. The CTCAE reporting guidelines and grading details are available on the Cancer Therapy Evaluation Program website.

The subset of AEs considered by the investigator to be related to study drug will be considered to be treatment-related AEs. If the investigator does not specify the relationship of the AE to study drug, the AE will be considered to be treatment-related. The incidence of AEs and treatment-related AEs will be tabulated. In addition, serious TEAEs will also be tabulated.

Any missing onset date, causality, or severity must be queried for resolution. Unresolved missing causality and severity will be handled according to the following rules:

- An unresolved missing causality will be considered treatment-related.
- An unresolved missing severity will be identified as an unknown severity.

For purposes of analysis, all AEs will be considered TEAEs unless the AE can unequivocally be defined as not treatment-emergent.

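### The safety follow-up waiver in Protocol 8.8.1 is set by visit label, so stopping at Week 28 can leave the last scheduled contact 1–2 days (nominal) before the 30-day adverse-event window closes

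*Protocol*

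**What the plan says.** **The waiver.** Protocol Section 8.8.1 places the follow-up visit 30 (+7) days after the Week 32 or early-termination visit. It then releases one group, stating that those in "an observation/no treatment cycle from Week 28 or earlier until Week 32 do not need to complete the safety follow-up visit". No minimum number of days since the last application is attached.

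**The 30-day window.** The next paragraph of the same section states that "Adverse events and SAEs must be reported up until 1) at least 30 days after the last application of study drug", or for longer if toxicities have not resolved. Section 8.3.1 has adverse events monitored "until at least 30 days after the last application of study drug". SAP Section 9.2.1 defines a treatment-emergent event as one arising or worsening "after first application of study drug and within 30 days of the last application of study drug". The follow-up column of Protocol Table 3 is headed "30 days (+ 7) days after last application".

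**How treatment can end at Week 28.** Section 6.1 provides for open-label participants who have cleared (AN count 0 and Skin Pain NRS 0). If the stopping point falls at a study visit, then, "as assessed by the investigator, treatment is to be stopped at the study visit".

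**How events in the last days are to be collected.** Section 8.8.1 relies on the follow-up visit: "Reasonable efforts should be made to have the participant return for the follow-up visit and report any AEs that may occur during this period". It names no telephone call or other contact for participants who are excused. Section 8.6 allows unscheduled visits when medically warranted.

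**The concern.** The waiver makes sense if the Week 32 visit already serves as the post-treatment safety visit. For that to hold, Week 32 must fall at or beyond the end of the 30-day window. Four weeks is 28 days, so at its own boundary the rule falls just short of the standard stated in the same section. A participant who stops on the Week 28 visit day and stays off treatment is last asked about adverse events at Week 32, nominally before the window closes, and no later contact is planned.

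What is at stake is how completely adverse events are found in the last days of the window for that participant. An event starting on day 29 or 30 would be reportable and would count as treatment-emergent, but it would be found only if the participant volunteered it or the site made contact on its own initiative.

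**Working it through.** The 30 days is a rule rather than a derived figure, so there is nothing to reproduce for it. The protocol's overall duration can be checked: 28 days of screening + 16 × 7 + 16 × 7 days of treatment + 30 days of follow-up = 282 days, and 282 / 7 = 40.3 weeks. This agrees with the approximately 40 weeks in Section 4.2.

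**Inputs**
- Required window: 30 days after last application (Protocol 8.3.1 and 8.8.1; SAP 9.2.1).
- Nominal interval between the Week 28 and Week 32 visits: 4 × 7 = 28 days.
- Visit windows: ±3 days at each visit (Table 3).
- *n* = days from last application to the Week 28 visit (0 = same day, 1 = the day before).
- *a*, *b* = deviations of the Week 28 and Week 32 visits from their target days, each between −3 and +3.

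**Formulas**
- Nominal interval = 28 + *n*.
- Both windows anchored to Day 1: interval = 28 + *n* + *b* − *a*, which runs from 22 + *n* to 34 + *n*.
- Week 32 scheduled from the actual Week 28 visit: interval = 28 + *n* + *b*, which runs from 25 + *n* to 31 + *n*.

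The available text does not say which anchoring applies, so both are shown.

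| *n* | Nominal interval (days) | Nominal shortfall against 30 | Range, both anchored to Day 1 | Range, anchored to actual Week 28 |
|---|---|---|---|---|
| 0 | 28 | 2 | 22–34 | 25–31 |
| 1 | 29 | 1 | 23–35 | 26–32 |
| 2 | 30 | 0 | 24–36 | 27–33 |
| 5 | 33 | 0 | 27–39 | 30–36 |
| 8 | 36 | 0 | 30–42 | 33–39 |

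**Results**
- With on-time visits there is a shortfall only for *n* = 0 or 1: 2 days or 1 day.
- The largest possible shortfall is 30 − 22 = 8 days under Day 1 anchoring. It requires Week 28 three days late, Week 32 three days early, and a last application on the Week 28 visit day. Under the other anchoring the maximum is 30 − 25 = 5 days.
- The windows can also remove the shortfall: at *n* = 0 the interval can reach 34 days (or 31).
- No shortfall is possible once the last application is 8 or more days before Week 28 (Day 1 anchoring), or 5 or more days before it (the other anchoring).

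**Against the Table 3 heading.** A follow-up contact 30 (+7) days after last application falls on days 30–37. For *n* = 0, nominal Week 32 is day 28, 2 days before that interval opens.

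**If the visit were held as 8.8.1 dates it.** It would fall 28 + 30 = 58 to 28 + 37 = 65 days after the last application.

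**The case against.** The strongest reply is that no safety obligation is shortened. The waiver removes a visit and leaves the reporting duty in 8.8.1 and 8.3.1 intact, and Section 9.4 separately requires serious events to be reported within 24 hours. The wording is permissive, so a site may still hold the visit, and unscheduled visits remain open. SAP 9.2.1 counts every adverse event as treatment-emergent unless it clearly is not, so a reported late event would not be lost from the analysis. All of this stands, and it limits the point to scheduled ascertainment. None of it creates a planned contact at day 30.

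A second reply is that the waiver has a sensible purpose. Dated from Week 32, the follow-up visit would come 58–65 days after a Week 28 stop, and the Week 32 visit already includes adverse-event review, vital signs, examination and laboratory tests about four weeks off drug. This also stands. It is a reason to keep the waiver and tie it to the day count.

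Three stronger readings are tempting, and the documents do not support them.
- *That the gap is typically about a week.* Eight days is the extreme corner of the two visit windows under one anchoring. At *n* = 0, 34 of the 49 window combinations fall under 30 days, but that is a count of combinations. Reading it as a rate would assume independent, uniform visit timing, which nothing in the documents supports.
- *That the plan cuts the 30-day safety window or biases the treatment-emergent analysis.* The window and its definition are unchanged.
- *That the 28-versus-30-day mismatch causes a gap in pregnancy testing.* Table 3 footnote h says "Female participants of childbearing potential will have a serum test at screening and follow-up and a urine test at other visits noted", so a waived visit takes the follow-up serum test with it. But that happens to every excused woman of childbearing potential, however long she has been off drug. Table 9 differs from the footnote: it asks for serum at screening only and urine at all other visits. The 30 days in inclusion criterion 8b is a contraception commitment and does not require a test on day 30. Any question about pregnancy testing is separate from this point.

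**Conclusion.** The point holds, and it is small. Because the waiver is written in visit labels, a participant whose last application is on the Week 28 visit day or the day before has the last scheduled contact at nominally day 28 or 29, 1–2 days before the 30-day window closes, with no replacement contact written.

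This rests on two assumptions. First, a stop at the Week 28 visit counts as being off treatment from Week 28, which is the natural reading of 8.8.1 together with 6.1. Second, visits occur on time; the ±3-day windows can lengthen or remove the shortfall, as shown.

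Only open-label participants who have cleared, stop at or close to Week 28 and stay off treatment to Week 32 are affected. The documents give no number for them. They would come from approximately 60 randomized participants and may be very few or none. The primary endpoint and the double-blind safety comparison are unaffected. This is an optional tidying of safety follow-up; the trial's conclusions do not depend on it.

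**What to change.** In Section 8.8.1, allow the waiver only if at least 30 days have passed since the last application by the Week 32 visit. Otherwise require a telephone contact about adverse events at day 30 or later after the last application; the 7-day allowance in Table 3 could serve as its upper limit.

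For a stop on the Week 28 visit day with on-time visits, the call would be due from 30 − 28 = 2 days after Week 32. At the shortest interval the windows allow, it would be due from 30 − 22 = 8 days after. Participants off treatment well before Week 28 would still be excused.

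The cost is one sentence in the protocol and, in conduct, a brief call for a few open-label participants at most. No change to the SAP is needed, since its treatment-emergent window is already 30 days.
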